2.2 Supporting Data

2.2.1 Thiamine dose

In our previous study, the dose of benfotiamine administered to study animals was 70mg/kg body weight/day. The bioavailability of benfotiamine, which is fat soluble, is higher than that of oral soluble thiamine and there is corresponding higher plasma concentrations found for similar doses.

In one study of health volunteers, a single 40mg oral dose of benfotiamine lead to a plasma area under the concentration time curve (AUC) of 240 (standard deviation (sd) 22.9) h.ng/ml compared to 154.3 (sd 18.7) h.ng/ml for a single 100mg oral dose of thiamine mononitrate.¹³ Maximum plasma concentration was 64.9 (sd 37.7) ng/ml for benfotiamine compared to 38.9 (sd 22.7) ng/ml for thiamine. Half life was not significantly different, at 2.9 (sd 2.8) hours for benfotiamine compared to 2.6 (2.5) hours for thiamine. This study implies that the thiamine dose should be 4.12 times the benfotiamine dose to achieve the same AUC.

A study in patients with end-stage renal disease found an AUC of 1491 h.ng/ml after 100mg oral benfotiamine compared to 355.1 after 100mg oral thiamine nitrate.¹⁴ Maximum plasma concentration was 81.9 ng/ml after benfotiamine compared to 21.3 ng/ml after thiamine, while the half life was 7.6 hours for benfotiamine compared to 8.3 hours for thiamine. This gives a very similar value to before, of a 4.3 times higher AUC for benfotiamine than thiamine at the same dose.

Assuming a ratio of 4.2:1 thiamine dose:benfotiamine dose would give a similar AUC, this equates to 294mg/kg/day for our subjects. For an 80kg participant, this equates to 23,520mg/day. This is far in excess of the current maximum reported doses (7 – 8g/day). We therefore chose a lower dose of 1000mg twice a day (total daily dose 2000mg) to provide a dose higher than most replacement or treatment regimes, but still within previously reported safe dose limits.

Finally, previous views held that absorption of thiamine is by a saturable active transport mechanism in the small intestine, which limits oral absorption of high doses of thiamine. However a recent study examining the pharmacokinetics of high doses thiamine in healthy subjects showed that, contrary to these views, both saturable and non-saturable absorption exists.¹⁵ Doses up to 1500mg of thiamine hydrochloride (the formulation used in this study) led to a higher plasma AUC compared to doses of 500mg or 100mg, being 2046 h.ng/ml for the 1500mg dose, 623 for the 500mg dose, and 214 for the 100mg dose. Although this study was performed in healthy individuals, it is likely that similar non-saturable absorption would occurs in participants in our trial.

2.2.2 Potential risks of thiamine

Thiamine is a vitamin, being available in many different food groups as well as being available to buy without a prescription. Dietary supplementation is generally viewed as being low risk, with no specific toxic effects identified.¹²

A number of small studies performed in patients with Alzheimer's disease showed that high doses produce minimal side effects.¹⁶⁻¹⁸ The majority of the participants in these trials were treated with 3g/day, at which dose no adverse effects were seen. A small follow-on study of 17 patients were treated at doses of 4-8g/day over 3 to 13

months.¹⁸ No adverse effects were seen at doses up to 6g/day. A number of participants at higher doses (6g/day or higher) had some degree of neuromuscular blocking detected on electromyography (>10% of motor units), but this was asymptomatic and not clinically detectable. Above 7g/day, 2 participants developed nausea and indigestion, which settled on reducing the dose by 0.5g/day. Given the lack of toxicity at the proposed dose (2g/day), it is not thought likely that toxicity will develop over the 3-5 days of the study.

[figure not shown]
A report from 2003 by the Food Standards Agency in the United Kingdom reported that “Reports of thiamin-associated toxicity in humans are rare and most relate to incidents following parenteral administration of the vitamin. High doses (≥ 5000 mg) of thiamin hydrochloride may cause headache, nausea, irritability, insomnia, rapid pulse and weakness; these symptoms are relieved following cessation of treatment or reduction of dose.”¹²

2.2.3 Potential risks of study procedures (right atrial appendage retrieval/left ventricular biopsy)

As part of the study, the right atrial appendage and a left ventricular biopsy will be obtained. These procedures have been part of the observational study since 2012 (right atrial appendage) and 2013 (left ventricular biopsy). The right atrial appendage is removed as part of the normal operating procedure for CABG and so does not entail any additional risk – this tissue is otherwise simply discarded. Left ventricular biopsy is not part of the normal operating procedure for CABG but entails minimal risk. In the appendix are two documents submitted with the application for amendment to the observational study covering this procedure, a letter of support from [name] regarding the safety of the procedure, and a scientific statement regarding the procedure. Over the time period of the observational study, there have been no episodes of harm related to these procedures. As we are not changing any part of the procedures involved with this aspect of the observational study, there is no additional risk related to the procedures compared to the observational study alone.

3 STUDY DESIGN

The study design is that of a randomised trial, stratified by diabetes status, as shown in the following figure.

4 SELECTION AND ENROLLMENT OF SUBJECTS

4.1 **Inclusion Criteria**

1. Patients listed for inpatient coronary artery bypass surgery due to atherosclerotic coronary artery disease *and*
2. Aged 50 years and over *and*
3. Left ventricular systolic function normal on echocardiography (ejection fraction \geq 50%) performed during this inpatient stay (or within three months if no myocardial infarction has occurred between date of echocardiogram and date of enrollment).

4.2 **Exclusion Criteria**

1. Left ventricular systolic function impaired (echocardiographic ejection fraction $<$ 50%) *or*
2. Renal failure with creatinine $>$ 200 $\mu\text{mol/l}$ or requiring renal replacement therapy *or*
3. Already taking thiamine supplementation *or*
4. Previously had an adverse reaction to thiamine, or a supplement or medication containing thiamine *or*

5. Previous or current history of alcohol related problems. This refers to a previous diagnosis of a medical condition thought to be caused or exacerbated by alcohol, or harmful use of alcohol (International Classification of Diseases version 10 codes F10.0 to F10.9) *or*
6. Other major medical conditions that, in the opinion of the investigator, would make randomisation of the participant to thiamine unsafe or undesirable.

4.3 **Study Enrollment Procedures**

- Potential participants will be identified on release of the inpatient cardiac surgery list.
- These potential participants will be approached by a study nurse with information about the study.
- Potential participants will be given an appropriate period of time to consider whether to take part, depending on their prior knowledge of the observational study.
- If willing to take part, the potential participant will be screened according to the criteria above, with the screening recorded for future use.
- If eligible for the study, the potential participant will then be asked to sign a consent form.
- After consenting, the study nurse will obtain a baseline history and record investigations obtained as part of routine clinical care.
- The participant will then be randomised, with the initial treatment to be given at 6pm the evening of enrollment and the final treatment to be given the morning of the procedure.
- Study drug will have been prelabelled by the Clinical Trials Pharmacist with a unique code, and so the study drug will be allocated sequentially by study nurses to participants, based on diabetes status. The Cardiology Research Nurses will record the medication label and add the participant's name and the date to the medication packaging.

5 **STUDY INTERVENTIONS**

5.1 **Interventions, Administration, and Duration**

If allocated to active treatment, 1000mg (2 x 500mg capsules, Pharmaceutical Compounding NZ Ltd, Auckland) of thiamine will be administered orally twice a day, with the initial dose to be at approximately 6pm no more than 5 days before CABG. No side effects are expected at this dose, but potential side effects seen at higher doses are nausea, headache, irritability, insomnia, rapid pulse and weakness. If these occur, the active treatment may be stopped. If allocated to placebo treatment, 2 x matching placebo capsules (containing maltodextrin 500mg each) will be administered following the same regime as active treatment (Pharmaceutical Compounding NZ Ltd, Auckland). Capsules will be prepacked into bottles of 20. Active and placebo medications will be identical, both medications being dry powder in size 00 natural gelatin capsules. The Thiamine HCl (USP) is been purchased by Pharmaceutical Compounding NZ Ltd from Medisca (Australia), a specialist supplier of ingredients for compounding pharmacies. Medisca hold a TGA Licence to Repack Therapeutic Goods; and as such operate a testing and quality assurance system to ensure that all materials supplied meet the appropriate specification.

In the event of predicted postponement of CABG after randomisation, four and a half days of study drug (active or placebo) should be completed, i.e. 9 administrations of study drug equal to 18 capsules. The final further single 1000mg dose of study drug (2 x 500mg thiamine capsule or 2 x placebo capsule) should then be administered the night before surgery. In the event of postponement of CABG after the full course has been taken (i.e. cancellation on the scheduled day of surgery), no further study drug needs to be taken.

5.2 **Handling of Study Interventions**

The interventions (thiamine/placebo) will be bought by the Southern District Health Board Clinical Trials pharmacist from Pharmaceutical Compounding NZ Ltd, Auckland. The capsules will be packed into 20 capsule bottles by Pharmaceutical Compounding NZ Ltd (Licenced Pharmacy). Deliveries to the Southern District Health Board will be in batches of 15 bottles of active intervention and 15 bottles of placebo at a time. They will be stored in the Cardiology Research Nurses office in a designated locked area designed for dispensing of study medication. This room is kept at 21-22 degrees Celsius, which should be sufficient to supply the supplied 6 month shelf life for the study drugs.

5.3 **Randomisation procedure**

Prior to delivery of study drug to the Cardiology Research Nurses, the Clinical Trials Pharmacist will label the study drugs. This will be based on a randomisation list generated from <http://www.randomization.com>, where we will use 5 blocks of 4 participants each for the diabetic and nondiabetic arms of the trial. After labeling the study drugs, the Clinical Trials Pharmacist will hold both hard and soft copies of the randomisation lists, which will only be made available to the study investigators at the time of statistical analysis, i.e. unblinding.

5.4 **Concomitant Interventions**

None

5.5 **Adherence Assessment**

Study nurses will assess the participants prior to CABG to determine adherence with medication, by means of a pill count and patient questioning. In addition, functional B1 assays will be performed as described in the laboratory evaluations below.

6 CLINICAL AND LABORATORY EVALUATIONS

6.1 *Schedule of Evaluations*

Evaluation	Screening	Pre-Entry	Entry	Day 3	Day 4	Day 5/day of CABG	Day 6 post CABG
Informed Consent		X					
Documentation of Disease/Disorder	X	X					
Medical/Treatment History	X	X					X
Clinical Assessment		X					
Laboratory results assessment		X					
Progenitor cell isolation						X	
Stored Plasma		X				X	X
Stored blood		X				X	X
Adherence Assessments			X	X	X		
Questionnaires - safety			X	X	X		X

6.2 *Timing of Evaluations*

This section should include definitions of the column headings in the Schedule of Evaluations and any special instructions.

6.2.1 Pre-Randomisation Evaluations

Screening will be performed as described above. No fixed time limit is required for this as long as a participant, if randomised to active treatment, will receive 3-5 days of treatment.

6.2.2 On-Study/On-Intervention Evaluations

At baseline, we will obtain 40ml of blood. This may be used for analysis of variables not already examined as part of the participant's clinical care (e.g. HbA1c). The majority of this blood will be stored for later comparison with the sample taken immediately prior to CABG. We will also obtain a standardized assessment of patient's health status and history. Routine laboratory test results already taken will be recorded as will echocardiogram and angiogram results.

On day three after randomisation and each subsequent day prior to the procedure, medication adherence and assessment of toxicity will be assessed. This will necessarily be a different number of days depending on when surgery has been scheduled.

Immediately before surgery (on the day of the procedure), a 40 ml blood sample will be taken. To ensure adequate absorption of oral thiamine has been achieved, a vitamin B1 assay will be carried out in all patients.

From this point on, the evaluation follows the same process as that already established in the observational study, which is included below under Laboratory Evaluations (Section 6.1.11).

6.2.3 Intervention Discontinuation Evaluations

If the participant wishes to discontinue active treatment, the adherence questionnaire and assessment of toxicity will be completed. Reason for discontinuation will be specified, and the participant will be invited to remain on study but off-intervention.

6.2.4 On Study/Off-Intervention Evaluations

If the participant is on study but off-intervention prior to CABG we will still retrieve the second blood sample prior to CABG as well as tissue for which consent has been granted. No active treatment is planned for after the time of CABG.

6.2.5 Final On-Study Evaluations

Prior to discharge on day 6 (i.e. the following Monday for those having CABG on Tuesday) the patient will be assessed for early in-hospital outcomes to monitor safety, in particular atrial fibrillation. Another blood sample will be taken for storage, especially to assess thiamine levels.

6.2.6 Off-Study Requirements

Once off-study, no further follow-up is planned, although consent will be requested for possible longer term follow-up using electronic records.

6.3 ***Special Instructions and Definitions of Evaluations***

6.3.1 Informed Consent

Once identified, potential participants will be given the Patient Information Leaflet to read by one of the study nurses. Any questions regarding the trial will be directed to one of the study nurses in the first instance. If the potential participant decides to take part, an investigator or an appropriate person delegated by the investigator to take consent will check understanding and, if satis-

fied that consent is valid, will countersign the consent form after the participant. “Appropriate person” refers to someone with sufficient experience and knowledge of the trial and trial processes to ensure accurate information is available to the potential participant – in practice, this is likely to be a cardiology study nurse, cardiology registrar, or cardiology consultant. Signed consent forms will be stored along with other study documentation by the cardiology research nurses.

6.3.2 Documentation of inclusion criteria

Presence on the CABG inpatient waiting list along with an angiogram report documenting atherosclerotic coronary artery disease suffices to demonstrate the disease inclusion criteria.

Exclusion criteria will be determined by examination of echocardiograph report and medical history. Inclusion and exclusion criteria will be completed on the screening log entry for each potential participant.

6.3.3 Medical/Treatment History

Medical history will be obtained by examining the medical record of the patient and discussion with the participant. A standard reporting form will be completed, documenting in particular previous history (especially presence and duration of diabetes), details of current presentation (especially non-ST elevation myocardial infarction vs unstable angina), and relevant tests (especially high sensitivity troponin, HbA1c). Documentation of current medications will be made.

Prior to discharge, brief assessment of development of post-operative complications, such as atrial fibrillation, will be made.

6.3.4 Clinical Assessments

At time of entry to study, brief assessment of physical status will be made, using the NYHA scale for heart failure symptoms and the Canadian Cardiovascular Society scale for angina symptoms. Heart rate, blood pressure, height and weight will be obtained from the medical charts.

6.3.5 Laboratory Evaluations

During the surgical procedure right atrial appendages are standardly excised for the insertion of a venous cannula to institute cardiac pulmonary bypass before cross clamping of the ascending aorta. Thus, collection of right atrial appendages does not require a change from the standard surgical protocol.

For the ventricular samples, an area of the anterior wall of the left ventricle (LV), free from any epicardial scarring following previous myocardial

infarction, will be identified. A wedge (1.5 x 1.5 x 10 mm) from the anterior wall of LV will be biopsied. The minimal amount of tissue needed for the protein analysis is 5 mg wet weight. The site will be sutured using a single pledgeted or non-pledgeted 4-0 prolene suture.

The protocol for isolation and culture of cardiac progenitor cells has been successfully established in the our laboratory and published.¹⁰ In brief, after serial washing to remove the blood, atrial appendage tissue will be digested with a mixture of collagenase type II and collagenase type IV (Worthington Biochem, USA) to prepare the single cell suspension. Next, the CD34 positive population, which indicates the circulating progenitor cells, will be depleted using a commercially available magnetic beads separation system (MACS separation columns, Miltenyi). CD90 and CD105 positive cells will then be enriched from the CD34 depleted population using the same system as above. The isolated cells will be cultured in the commercially available stem cells maintenance medium (Mitenyi). Using this protocol we regularly extract $0.5 \times 10^4 - 1 \times 10^4$ CD34-CD90⁺CD105⁺ cells per 100mg of tissue which can then be expanded for the required experiments. Importantly, these cells can be freeze stored for later use in the experiments. BrdU incorporation by the progenitor cells, a measure of cell proliferation, will be measured using a BrdU immunofluorescence assay kit from Roche, according to the manufacturer's instructions. Transketolase activity will be measured using a commercially available kit (Sigma).

6.3.6 Other Laboratory Studies

Other laboratories studies are likely to be carried out in the future as substudies, but are not part of the primary or secondary outcome measures of the trial. These may include, but are likely not to be limited to, further assessment of the metabolic changes in the tissue and blood of those receiving active treatment, relationship between genomic and epigenomic factors (such as specific single nucleotide variants and specific methylation patterns, respectively) and response to treatment, differences in expression due to active treatment of molecules and proteins relevant to diabetic cardiomyopathy (such as advanced glycation end-products or extracellular collage) or other diseases. After unblinding, the samples taken from those participants may be included with other participants for analysis in the observational study.

6.3.7 Toxicity Assessment

A brief questionnaire assessing potential side effects related to active treatment will be completed prior to participants undergoing CABG. Prior to discharge, a brief assessment of post-operative complications will be recorded.

6.3.8 Adherence Assessments

Adherence will be assessed by a brief questionnaire and a pill count.

7 MANAGEMENT OF ADVERSE EXPERIENCES

Adverse experiences related to the study intervention are expected to unlikely, for reasons discussed in section 2.2.2. These are:

- headache,
- nausea,
- irritability,
- insomnia, rapid pulse
- weakness

These can be treated in the usual form, as decided by the clinical team caring for the participant.

8 CRITERIA FOR INTERVENTION DISCONTINUATION

If the clinical team treating the patient believe any of these adverse experiences are related to the study intervention, they may stop the study intervention without further discussion with the study team. Study nurses will document details of cessation of treatment, including reason and progress after cessation, during their daily patient assessment prior to CABG. No unblinding is expected to be performed as a result of study intervention cessation, and further evaluations, in particular right atrial appendage and left ventricular biopsy, will be carried out as before.

9 STATISTICAL CONSIDERATIONS

9.1 **Outcomes**

9.1.1 Primary outcome

The primary outcome measure is the proliferation ability of resident cardiac stem cells, as measured by BrdU activity.

9.1.2 Secondary outcomes

Secondary outcomes are other functional measures, such as the ability to differentiate into cardiomyocytes, as measured by the number of GATA-4 and connexin-43 positive cells after exposure to differentiation medium, and measurement of the level of transketolase to determine the activation of pentose phosphate pathway

9.2 **Outcomes discussion**

Primary and secondary outcomes will be measured without knowledge of treatment assignment (i.e. blinded).

Bromodeoxyuridine (BrdU) is a thymidine analogue that is taken up by cells actively replicating DNA. As such it is widely used as an assay to determine proliferation of cells, and has appeared in over 20,000 biomedical science articles.¹⁹ In addition, we have demonstrated accuracy in our laboratory, with our animal studies demonstrating

a coefficient of variation of 9% in non-diabetic animals and 13-14% in diabetic animals. As such, it is a valid test to use to assess the function of resident CPCs.

9.3 **Sample Size and Accrual**

The primary outcome will initially be assessed in treated vs non-treated groups (combining diabetics with non-diabetics) and then stratified by diabetic status. We therefore calculated a sample size powered by subgroup (diabetic vs non-diabetic) status. Based on our previous data, with a sample size of 10 in each group (non-diabetic no active treatment, non-diabetic active treatment, diabetic no active treatment, diabetic active treatment) giving a total of 40 patients in total, we will have 99% power and 91% power, in non-diabetics and diabetics respectively, to detect a two-tailed 30% difference in primary outcome with treatment at a significance level of 0.05. Here we use a t-test to compare groups, with data coming from assessment of BrdU activity in CPCs isolated from treated and untreated animals.¹⁰ Note that we may have higher power, as we detected a 79% and 106% increase in mean proliferation activity of stem cells in treated non-diabetic and diabetic animals, respectively, compared with control. However given the uncertainty moving from an animal model to humans, we felt it prudent not to limit groups to less than 10 patients each.

Accrual rate is expected to be approximately 1-2 participants per fortnight. This is based on current accrual rates of 2-4 participants per fortnight in the observational study – many of these will be eligible for inclusion in this trial and are likely to volunteer based on the low toxicity of the intervention. Given the exclusion of the highest risk cases (those with impaired left ventricular systolic function or those undergoing cardiac surgery on an emergency basis) and the short duration of treatment, we expect the vast majority of those enrolled to complete allocated treatment until CABG, i.e. a low loss to follow-up rate.

9.4 **Data Monitoring**

An interim blinded analysis of the toxicity data will be performed after recruitment of 20 patients by the study team. We expect there to be few adverse experiences on or off active treatment. If more than 20% of participants report adverse experiences, then a separate Data and Safety Monitoring Board will be recruited consisting of at least two clinicians independent of the investigators. These will be supplied with the toxicity data and the unblinding codes, if required. If, in their opinion, excess toxicity is seen with active treatment, a recommendation to halt the trial can be made to the study investigators.

An interim analysis of study recruitment will be made one year after randomisation of the first subject. If recruitment is less than 20 subjects, we will attempt to assess the cause of this slow recruitment. This will be done by comparing with recruitment to the observational study and analysis of screening logs. If study validity can be maintained, an amendment to the study will be made to rectify perceived causes of slow recruitment.

No interim analysis will be made for primary or secondary outcomes given the small number of study participants.

9.5 **Data Analyses**

A standard two-tailed t-test will be used to compare the primary outcome between treated and non-treated groups, using an intention-to-treat analysis. Separate analysis of the primary outcomes stratified by diabetic status will be performed using a t-test. For secondary analyses, differences across multiple groups will be assessed using an analysis of variance (ANOVA) test followed by a Šidák-Holm multiple comparison test. Comparison between two groups will be assessed using t-tests.

Missing data will be removed from individual analyses, while not removing the entirety of the participant's data from further analysis. As mentioned above, loss to follow-up is expected to be low as participants are inpatients with short study duration.

10 **DATA COLLECTION, SITE MONITORING, AND ADVERSE EXPERIENCE REPORTING**

10.1 **Records**

Cardiology research nurses will keep records of screening, consent forms, medical/interventional history, adherence, and toxicity. Department of Physiology, University of Otago will keep records of blood samples obtained, tissue samples obtained, and results of blood and tissue analysis. All of these will be kept in locked areas, with no access to the public. Records will be kept for a minimum of 15 years in case these data require re-examination.

10.2 **Role of Data Management**

At study completion, study investigators will combine the records kept by the Cardiology research nurses and the Department of Physiology. The database will then be unblinded and statistical analyses described above carried out.

10.3 **Quality Assurance**

The Coordinating Investigator will ensure the cardiology research nurses are trained and equipped to perform their duties in the study. Laboratory protocols will follow standard laboratory methods for quality assurance. A random sample of participants clinical, echocardiographic and angiographic data will be checked for accuracy.

10.4 **Adverse Experience Reporting**

Serious adverse events will almost certainly be related to the participant's underlying diagnosis (i.e. admission with acute coronary syndrome) rather than the use of the interventional medicine. Adverse experiences are therefore reported to the Coordinating Investigator as soon as possible, within one month for non-serious adverse events and within one week for serious adverse events. Under their Standard Operat-

ing Procedures (May 2012) adverse events are not, in general, individually reported to the Health and Disability Ethics Committee, but are reported annually. The exceptions are in the event of urgent safety measures being required or a temporary halt to the study is required, in which case the Committee will be notified immediately (with seven days being the time limit specified by the Committee).

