The number of patients to be randomised in total is 40. Randomisation will be stratified based on diabetic status (non-diabetic/diabetic). The study population will be those patients admitted to hospital and awaiting urgent (i.e. inpatient) coronary artery bypass surgery, without valvular heart disease requiring intervention.

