The trial is based on our previous research showing that treatment with benfotiamine, a fat-soluble analogue of thiamine, increases the proliferation of resident cardiac progenitor cells (CPCs).¹⁰ In this study, CPCs from animals treated with benfotiamine had an improvement in proliferation of these progenitor cells as measured by the BrdU assay. This was seen in both diabetic and non-diabetic animals, but CPCs from diabetic animals had impaired proliferation ability at baseline. In addition, diabetic animals had lower number of CPCs than non-diabetic animals, and this also improved with benfotiamine. In CPCs isolated from humans, benfotiamine protected CPC proliferation ability when cultured in high glucose medium.

While benfotiamine, a lipid-soluble analogue of thiamine, was used for our pre-clinical studies, this has not been used in high doses in humans before. Although previous studies have not shown any major adverse effects from benfotiamine use even up to a dose of 400mg/day, a report for the European Food Safety Authority concluded that there was insufficient data to demonstrate the safety of benfotiamine as a source of vitamin B1 to be added to food supplements (which is how over the counter vitamins are regulated in the European Union).¹¹ We elected to use oral free thiamine, given its long history of safe use and assessment of toxicity as generally being viewed as “very low”.¹²

We have chosen a “real world” duration of intervention. Approximately 20-50% of coronary artery bypass surgery procedures are performed on patients with an acuity level of “urgent”, where the patient has been admitted to hospital with an acute unscheduled presentation and is to remain in hospital until the procedure is completed. These patients are necessarily higher risk than elective patients, but are generally stable enough to allow a period of 3-5 days of medical intervention prior to surgery. It is during this period, after the patient has been listed for surgery, that consenting patients will be randomised in the trial.

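### The overall primary t-test leaves out the diabetes stratum used for randomisation, so it is conservative and loses power to the extent that diabetics and non-diabetics differ

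*Protocol*

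**What the plan says.** Section 1.6 stratifies randomisation by diabetic status. Section 5.3 gives the mechanism: "we will use 5 blocks of 4 participants each for the diabetic and nondiabetic arms of the trial". Section 9.3 plans "with a sample size of 10 in each group" for the four treatment-by-diabetes cells, 40 patients in all, so each stratum is split 1:1.

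For the analysis, section 9.3 says: "The primary outcome will initially be assessed in treated vs non-treated groups (combining diabetics with non-diabetics) and then stratified by diabetic status". Section 9.5 names the test for the overall comparison: "A standard two-tailed t-test will be used to compare the primary outcome between treated and non-treated groups, using an intention-to-treat analysis". It then adds: "Separate analysis of the primary outcomes stratified by diabetic status will be performed using a t-test". ANOVA is named only for secondary analyses. No model with both treatment and diabetes is specified for the primary outcome.

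The protocol treats diabetes as prognostic for this endpoint. In the animal work described in section 2.1, "CPCs from diabetic animals had impaired proliferation ability at baseline". Section 1.4 lists as a trial hypothesis that diabetics on placebo have fewer and less functional progenitor cells than non-diabetics on placebo. Neither place gives the size of the deficit.

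**The concern.** Blocking within strata balances the arms on diabetes, so the diabetic deficit cancels out of the treated-minus-control difference. A two-sample t-test on the merged data does not know this. It estimates its error variance from the spread within each arm, and that spread includes the distance between diabetics and non-diabetics. The standard error is therefore larger than the true sampling error of the difference.

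The larger the diabetic deficit that motivates the stratification, the weaker the main test of thiamine becomes. What is at stake is a missed or blurred treatment effect in a 40-patient trial that takes ventricular biopsies. The protocol itself fixes the test, so this is not a detail left open for a later analysis plan.

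**Working it through.** **Inputs from the protocol.** 10 per cell in four cells; 30% difference; two-sided 0.05; stated power 99% (non-diabetic) and 91% (diabetic), all from section 9.3. Animal CVs of 9% and 13–14% are in section 9.2.

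**Assumptions.** Non-diabetic control mean 1; diabetic control mean 1 − g, with g = 0.20, 0.30 or 0.40; effect proportional (30% in each stratum); same SD in treated and control patients of a stratum.

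**The plan's own power figures.** For 10 against 10 (noncentral t, 18 df), the standardised effect is 0.30/CV.
- CV 9%: 0.30/0.09 = 3.33, power above 99.9% (stated 99%).
- CV 13–14%: 0.30/0.13 = 2.31 and 0.30/0.14 = 2.14, power 99.8% and 99.5% (stated 91%).

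The 91% does not follow from the printed CVs. Solving backwards, 99% needs a standardised effect of 2.03, so SD = 0.30/2.03 = 0.148. 91% needs 1.56, so SD = 0.30/1.56 = 0.192. These implied SDs are used below because they are less favourable to the trial than the printed CVs.

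**Variance inflation.** Let w be the average within-stratum variance. Each arm is half diabetic, so the pooled variance is about w + g²/4, an inflation of 1 + g²/(4w). With the SDs fixed at 0.148 and 0.192, w = (0.0219 + 0.0369)/2 = 0.0294, with root 0.171.

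| Gap g | g²/4 | Inflation of variance | Inflation of CI width |
|---|---|---|---|
| 20% | 0.0100 | 1.34 | 1.16 |
| 30% | 0.0225 | 1.77 | 1.33 |
| 40% | 0.0400 | 2.36 | 1.54 |

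**Hand check at g = 30%, SD fixed.** The true standard error of the arm difference is 0.171 × √(2/20) = 0.0542.
- No effect: the t-test uses √(0.0294 + 0.0225) × √(2/20) = 0.0720. With the critical value 2.02 (38 df), it rejects beyond 0.146, which is 2.69 true standard errors. Type I error is about 0.7%.
- 30% effect: the average difference is 0.30 × (1 + 0.70)/2 = 0.255. The stratum gap is 0.30 in controls and 0.39 in treated patients, so the pooled variance is 0.0294 + (0.09 + 0.152)/8 = 0.0596. The test's standard error is 0.0772 and its threshold 0.156. Power is about Φ((0.255 − 0.156)/0.0542) = Φ(1.82) = 97%.

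Simulation, which also allows for estimation of the variance, gives 0.9% and 95.6%.

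**Simulation results** (10 per cell; planned t-test against a linear model on treatment + stratum, 37 df):

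| Scenario | Gap 20% | Gap 30% | Gap 40% |
|---|---|---|---|
| Type I error, t-test, SD fixed | 2.4% | 0.9% | 0.2% |
| Type I error, t-test, SD proportional to mean | 1.8% | 0.5% | under 0.1% |
| Power, 30% effect, SD fixed: t-test | 99.3% | 95.6% | 82.2% |
| Same, with stratum term | 99.8% | 99.4% | 98.9% |
| Power, 30% effect, SD proportional: t-test | 99.8% | 99.1% | 93.6% |
| Same, with stratum term | about 100% | about 100% | about 100% |
| Power, 30% effect, CV 30% in both strata (assumed): t-test | 82% | 74% | 61% |
| Same, with stratum term | 85–87% | 85–87% | 85–87% |

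The stratum-adjusted test has a type I error of about 5% throughout. With no gap, both tests have 5.0% and equal power, so the whole difference comes from omitting the stratum.

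**The case against.** The strongest reply is that little is lost at the trial's own design point. At a 30% effect with the implied SDs, a 20% gap costs at most about half a point of power. With the CVs printed in section 9.2, power stays at 99.7% or above even at a 40% gap. The gap itself is assumed, since the protocol states only its direction. This stands, and it limits the severity.

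The second reply is that the sample size was set by subgroup and section 9.5 plans a t-test within each stratum. A difference between strata cannot enter the error term of those tests, so an effect missed in the merged analysis could still appear there. This also stands in part. But each of those tests uses 20 patients, and they do not repair the p-value or confidence interval of the overall comparison, which comes first.

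A reader might infer from an error rate that is not 5% that false positives are more likely, or that the estimate is confounded by diabetes. Neither follows. In these scenarios the error rate is at or below the nominal level, and 1:1 allocation within strata keeps the estimate unbiased.

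A reader might also quote a starker contrast: for a 20% effect with SD proportional to the mean, power is about 89/73/43% against 96% with the stratum term. Those figures are arithmetically sound, but the protocol nowhere plans for a 20% effect, so they illustrate sensitivity and do not describe the design.

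**Conclusion.** The point holds as a matter of efficiency and calibration. The overall primary test is conservative, its interval is too wide, and it loses power whenever diabetics and non-diabetics differ. At the protocol's 30% effect and implied SDs, the loss at gaps of 20/30/40% is about 0/1/6 points if the diabetic SD scales with the mean, or about 0.5/4/17 points if it does not. It is larger if human variability is greater or the effect smaller. Section 9.3 allows for that possibility when it cites the uncertainty of moving from animals to humans.

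The size rests on an assumed gap and on SDs back-calculated from the stated power. The direction needs only that the strata differ, which the protocol expects.

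Severity: should fix. The documents do not support calling the trial invalid or underpowered at its design effect on this ground. Nor do they support requiring a log scale, or imposing the same model on every secondary outcome: they say nothing about the distribution of BrdU, and section 9.5 already plans ANOVA for the secondary analyses.

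**What to change.** In section 9.5, replace the overall primary t-test with wording such as: the overall comparison of BrdU activity will use a linear model (two-way ANOVA) with treatment and diabetes stratum as randomised; the treatment coefficient, its 95% confidence interval and its two-sided p-value are the primary result. Keep the planned t-tests within each stratum. Align the sentence in section 9.3 that describes the combined comparison.

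The change uses one degree of freedom (37 instead of 38) and needs no further patients or data. It should be made before unblinding, so that the choice of model cannot depend on the results.
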